1. OVERVIEW

1.1. Background

Duchenne muscular dystrophy (DMD) is a disabling and life-threatening X-linked genetic disorder [Worton 2001, Khurana 2003] caused by defects in the gene for dystrophin, a protein that stabilizes muscle cell membranes [Lapidos 2004]. Due to muscle fragility, boys with DMD develop muscle weakness that leads to deterioration of ambulation, wheelchair dependency, and eventual respiratory and cardiac failure with death by 15 to 22 years of age [Brooke 1989, McDonald 1995, Worton 2001]. Most patients are characterized as having Duchenne muscular dystrophy and experience onset of symptoms during early childhood [Ciafaloni 2009]. A small subset (~10%) of boys is classified as having Becker muscular dystrophy (BMD), a phenotypically milder form of dystrophinopathy that is associated with later manifestation of symptoms [Emery 1991]. Only chronic administration of corticosteroids has slowed progression of dystrophinopathy. However, corticosteroids do not address the underlying cause of dystrophinopathy, are typically associated with serious sequelae, and are not always employed. There is no current therapy for the underlying cause of dystrophinopathy. In ~13% of boys with Duchenne/Becker muscular dystrophy (DBMD), the causative defect in the dystrophin gene is a nonsense mutation that truncates dystrophin protein production by introducing a premature stop codon into the dystrophin messenger ribonucleic acid (mRNA) [Dent 2005]. Nonsense mutation DBMD (nmDBMD) is estimated to affect ~1700 boys in the United States and ~2200 boys in Europe [Hirawat 2004a, Hirawat 2004b].

Ataluren is an orally bioavailable, investigational new drug that promotes ribosomal readthrough of premature stop codons [Welch 2007, Du 2008, Wang 2010, Goldmann 2011, Tan 2011, Kayali 2012]. In reporter assays, as well as in nonclinical models of genetic disease, ataluren demonstrates the ability to specifically and selectively enable ribosomal readthrough of mRNA containing a premature stop codon, inducing production of protein that localizes to the appropriate cellular location and is functionally active [Welch 2007, Du 2008, Wang 2010, Goldmann 2011, Tan 2011, Kayali 2012]. In vitro and in vivo studies in nmDBMD have shown that ataluren can restore production of the missing dystrophin [Welch 2007, Kayali 2012].

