Patients completing Study 007 were eligible to enroll in an open-label extension trial PTC124-GD-007e-DMD (Study 007e). Of the 174 patients participating in the blinded Phase 2b study,

173 patients enrolled in this study. These patients received the 20-, 20-, 40-mg/kg dose level of ataluren for a median [range] of 22 [11 to 57] weeks before the study was discontinued on 03 March 2010. The safety findings from this study confirmed that ataluren was well tolerated; there were no concerning safety signals evident in the patients participating in this trial.

Patients completing Study 004 were eligible to enroll in an open-label extension trial. Of the 38 patients participating in the prior Phase 2a study, 36 patients enrolled in an open-label extension study PTC124-GD-004e-DMD (Study 004e). These patients received the 20-, 20-, 40-mg/kg dose level of ataluren for a median [range] of 70 [53 to 81] weeks before the study was discontinued on 03 March 2010. The safety results from this trial also documented good tolerability for ataluren; there were no worrisome ataluren-related adverse events reported for the patients participating in this trial.

In addition, an open-label Phase 2a study PTC124-GD-008-DMD (Study 008) was conducted in nonambulatory patients with nmDBMD; this study was discontinued on 03 March 2010. At the time of discontinuation, 6 patients had received the 20, 20, 40 mg/kg dose level of ataluren for periods ranging from 1 week to 6 weeks. While no safety concerns were identified during this study, with the small number of patients and short duration of dosing, no definitive conclusions can be drawn from this study regarding the safety profile of ataluren 20, 20, and 40 mg/kg in nonambulatory boys with nmDBMD.

The results of the nmDBMD program were reviewed by an independent DMC on 24 February 2010. It was the DMC opinion that there were no safety concerns based on the available data.

Ongoing Study PTC124-GD-016-DMD

A Phase 3 open-label, study PTC124-GD-016-DMD (Study 016) to assess the safety of ataluren in patients who participated in one of the 5 previous ataluren nmDBMD studies at an investigator site in the US is ongoing. As of 01 September 2015, this study had enrolled 108 patients who received ataluren for a median of 124 weeks (range, 4 to 249 weeks).

Ongoing Study PTC124-GD-019-DMD

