A Phase 3 open-label, study PTC124-GD-019-DMD (Study 019) to assess ataluren in patients who participated in one of the 5 previous ataluren nmDBMD studies at an investigator site in Europe, Israel, Australia and Canada is ongoing. As of 11 November 2015, this study has enrolled 95 patients who received ataluren for a median of 128 weeks (range, 16 to 166 weeks).

Safety Experience in Other Indications

Ataluren is currently being evaluated in children and adults with nonsense mutation cystic fibrosis. Detailed descriptions of these studies and safety information from them are provided in the Ataluren Investigator Brochure.

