## **8. CINRG DATA**

### **8.1. Overview of CINRG Data**

CINRG is a natural history registry database which collects DMD data using consortium of medical and scientific investigators from academic and research centers on neuromuscular disease. Demographics and baseline characteristics, corticosteroids medication use (and type), efficacy endpoints including 6MWT, time taken to stand from supine, time taken to run/walk 10 meters, NSAA, spirometry, and EK will be analyzed. Other endpoints collected by CINRG but not in Study 020e will not be included into this analysis plan. The CINRG natural history control (data transferred on November 18, 2016) will be compared to ataluren's efficacy data to assess the ataluren's long-term treatment benefit.

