### **8.2. Matched Populations**

To compare CINRG with Study 020e, the matched populations are defined in the following table for different endpoints and analyses.

Endpoint/Analysis	Age (Years) at Study Entry	Age (Years) at Assessment	Steroid Use	Ambulation status	Exclude EXON 51 and 45	Baseline value	Visit Year
Age at loss of ambulation	7-14	Not applicable	Cumulative Steroid use duration at each assessment $\geq 6$ months	Ambulatory at study entry	Yes		Not applicable
Piece-wise regression based on FVC	Not applicable	$\leq 19$	Cumulative Steroid use duration at each assessment $\geq 24$ months	Non-ambulatory at each assessment	Yes	Not applicable	$\geq 2012$
%-predicted FVC	7-15	Not applicable	Not applicable	Non-ambulatory at study entry	Yes		Not applicable
%-predicted FEV1	7-15	Not applicable	Not applicable	Non-ambulatory at study entry	Yes		Not applicable
PEF	7-15	Not applicable	Not applicable	Non-ambulatory at study entry	Yes		Not applicable
6MWT	7-15	Not applicable	Cumulative Steroid use duration at each assessment $\geq 6$ months	Ambulatory at study entry	Yes		Not applicable
time taken to run/walk 10 meters	7-15	Not applicable	Cumulative Steroid use duration at each assessment $\geq 6$ months	Ambulatory at study entry	Yes		Not applicable
time taken to stand from supine	7-15	Not applicable	Cumulative Steroid use duration at each assessment $\geq 6$ months	Ambulatory at study entry	Yes		Not applicable
NSAA	7-15	Not applicable	Cumulative Steroid use duration at each assessment $\geq 6$ months	Ambulatory at study entry	Yes		Not applicable

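### SAP 8.2 defines the CINRG control with no rule on ataluren exposure, overlap with 020/020e, or nonsense mutation

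*Protocol*

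**What the plan says.** SAP 8.1 introduces the external control: "CINRG is a natural history registry database which collects DMD data using consortium of medical and scientific investigators". It gives the control's use and date: "The CINRG natural history control (data transferred on November 18, 2016) will be compared to ataluren's efficacy data", with the stated aim of assessing long-term benefit. SAP 1 places this comparison outside the CSR.

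SAP 8.2 contains the selection rules: "To compare CINRG with Study 020e, the matched populations are defined in the following table for different endpoints and analyses". The columns are age at entry, age at assessment, steroid use, ambulation status, an exon rule, baseline value and visit year. The exon rule, "Exclude EXON 51 and 45", is set to Yes in all nine rows and is the only genotype criterion. The visit-year limit (2012 onwards) applies only to the piece-wise FVC regression.

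SAP 8.3 lists the variables for judging comparability: age, race, ambulation, steroid use, duration and type, and baseline function. It takes each CINRG boy's first registry visit as his baseline.

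On the trial side, SAP 3.1 describes boys with nonsense mutation dystrophinopathy. Protocol 1.1 says that in about 13% of DBMD boys "the causative defect in the dystrophin gene is a nonsense mutation that truncates dystrophin protein production"; Protocol 2.2.1 gives 10-15%.

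Protocol 2.2.3 reports open-label use in US boys from earlier ataluren studies (Study 016): "As of 01 September 2015, this study had enrolled 108 patients who received ataluren for a median of 124 weeks". For Study 019, in Europe, Israel, Australia and Canada, it says: "As of 11 November 2015, this study has enrolled 95 patients who received ataluren for a median of 128 weeks". Protocol 10.1 expects about 220 boys in Study 020, and Protocol 1.1 dates its first dose to 10 April 2013.

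**The concern.** A natural history control should consist of boys observed without the drug. SAP 8.2 does not require this, although ataluren was being given to nonsense-mutation boys well before the registry data were transferred. Under the table as written, an exposed boy stays in the control, and a boy in both CINRG and 020e can appear on both sides. Nothing elsewhere closes the gap. Exclusion criterion 2 in Protocol 4.3 bars other therapeutic trials, which would not bar registry membership. Because CINRG baseline is the first registry visit, a boy could register untreated, start ataluren later, and keep contributing assessments.

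The second gap is mutation class. Every 020e boy has a nonsense mutation, while the controls are neither restricted to that class nor described by it.

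At stake is the plan's only comparison with boys outside the trial programme. Study 020e has no concurrent untreated arm, and SAP 7 removes the paired t-tests and the supportive 6MWT analyses. The primary safety analysis is not affected.

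**Working it through.** **1. Is there a rule anywhere?** SAP 8.1 to 8.3 is the only text on CINRG selection. None of the column headings in 8.2 covers ataluren exposure, trial enrolment or nonsense mutation. Mutation class is also absent from the 8.3 comparability list.

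**2. Could exposure and registry follow-up overlap in time?** Count back the longest exposure in each open-label study from its data date:
- Study 016: 1 September 2015 minus 249 weeks = 23 November 2010.
- Study 019: 11 November 2015 minus 166 weeks = 5 September 2012.
- Study 020: first dose 10 April 2013.

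All precede the transfer of 18 November 2016. The FVC row keeps visits from 2012 on, which are years in which ataluren was in use.

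**3. Reproduce the protocol's prevalence figures** (Protocol 1.1 and 2.1): 0.13 x 13,000 = 1,690 (stated about 1,700, US); 0.13 x 17,000 = 2,210 (stated about 2,200, Europe). The 13% figure is consistent with them.

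**4. Expected nonsense share of controls.** Let p be the nonsense share (10-15%, from the protocol) and x the fraction of the registry removed by the exon 51/45 rule. The documents do not give x; I assume 0 to 0.5, with only boys without a nonsense mutation removed. Share = p/(1 - x). Nonsense boys reach half of the controls when x = 1 - 2p.

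| p | x = 0 | x = 0.2 | x = 0.5 | x needed for half |
|---|---|---|---|---|
| 0.10 | 10% | 12.5% | 20% | 80% |
| 0.13 | 13% | 16.3% | 26% | 74% |
| 0.15 | 15% | 18.75% | 30% | 70% |

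So 70-90% of controls would be expected to have another mutation class. This reverses only if the exon rule removes 70-80% of the registry.

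**5. Expected share of exposed controls, if CINRG mirrors the population.**
- Study 016 against US DBMD: 108/13,000 = 0.8%; with x = 0.5, 108/6,500 = 1.7%.
- Studies 016, 019 and 020 against US plus EU DBMD: (108 + 95 + 220)/30,000 = 423/30,000 = 1.4%; with x = 0.5, 423/15,000 = 2.8%.

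This gives about 1-3%. It is rough: it ignores boys counted in more than one study, uses an expected enrolment for Study 020 and counts its placebo boys (who could move to ataluren in 020e), and sets worldwide enrolment against US and EU denominators.

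**6. Effect on a mean difference.** If a fraction c of controls is treated and gets the full effect, the difference is multiplied by 1 - c: 0.992 at c = 0.8%, 0.972 at c = 2.8%. This does not carry over exactly to Kaplan-Meier ages at loss of ambulation.

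**7. Price of restricting to nonsense mutation.** If a fraction f of controls is kept, the control-side standard error grows by 1/sqrt(f): 3.2-fold at f = 0.10, 2.8-fold at 0.13, 1.8-fold at 0.30. The CINRG sample size is not given, so no absolute number follows.

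**The case against.** The strongest reply is that contamination is conjecture. No document says that any CINRG boy took ataluren or joined 020/020e. SAP 8.1 calls the source a natural history registry, and the transferred data may already have been filtered. Even on population figures the effect is small, and it runs towards no difference, so it cannot create a false benefit. The two gaps also limit each other: these studies treated only nonsense-mutation boys, so if such boys are few among the controls, exposed controls are few as well. On genotype, nothing in the documents shows that nonsense-mutation boys progress differently from the controls left after the exon rule. Finally, the comparison is outside the CSR.

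Most of this stands as a limit on size. It does not supply the missing rule: the table is an explicit population definition, and "natural history" is a label, not a criterion.

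Two stronger readings go beyond the documents. A reader might infer that CINRG centres were also ataluren sites, so that most nonsense-mutation controls were treated. The documents name no CINRG centre and give no overlap. A reader might also infer, from the stop codon and exon location explorations in Protocol 10.5.1, that the sponsor regards mutation class as prognostic. Those were supportive 6MWT analyses within an all-nonsense population, and SAP 7 removed them.

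**Conclusion.** The omission is confirmed from the text: the CINRG control has no exposure rule, no overlap rule and no nonsense-mutation criterion, and mutation class is not tabulated. Whether any exposed or shared boy is actually in the control is unknown. If CINRG mirrors the protocol's population figures, about 1-3% of controls would be exposed, with a similarly small dilution towards no difference; a boy on both sides would also break the independence of the groups.

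Mutation class is the larger question. If CINRG mirrors the protocol's mutation mix, 70-90% of controls have another mutation class (assuming that the exon rule removes no more than half of the registry). A genotype contribution to any difference in FVC or age at loss of ambulation then cannot be ruled out, but neither its size nor its direction can be derived. A reader might conclude that an apparent benefit would be an artefact of genotype; the documents do not support that either.

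The point concerns the supplementary long-term benefit comparison only. It should be corrected before that comparison is used.

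**What to change.** - **SAP 8.2, all rows:** exclude CINRG boys enrolled in 020/020e; exclude, or censor from first dose, CINRG assessments after any ataluren exposure; report the number removed for each reason. The table already filters steroid duration at each assessment in several rows, so this has a familiar form. If the transferred data do not record ataluren use or trial enrolment, say so as a limitation.
- **SAP 8.3:** add mutation class to the comparability table.
- **Sensitivity analysis:** repeat the loss-of-ambulation and FVC comparisons in never-exposed CINRG boys with a nonsense mutation.

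The cost is SAP wording, a filter on registry treatment and mutation fields, and slightly fewer controls. The sensitivity analysis will have a wide interval (control-side standard error about 2.8 times larger if 13% of controls are kept), which is why it should sit beside the main comparison and not replace it. If the overlap is nil, the filter changes nothing and documents that fact.

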3. STUDY OBJECTIVE AND ENDPOINTS

3.1. Primary Objective

To evaluate the long-term safety of ataluren in boys with nonsense mutation dystrophinopathy, as determined by adverse events and laboratory abnormalities.

3.2. Secondary Objectives

The secondary objectives, which evaluate the effects of ataluren on major clinical manifestations of DMD, are:

Physical

- To determine the effect of ataluren on ambulation in patients who are ambulatory.
- To evaluate the effect of ataluren on proximal muscle function in patients who are able to perform timed function tests.
- To evaluate the effect of ataluren on physical function in patients who are able to perform the North Star Ambulatory Assessment.
- To evaluate the effect of ataluren on upper limb function.

Pulmonary function

- To evaluate the effect of ataluren on pulmonary function.

Patient-reported outcomes

- To determine the effect of ataluren on health-related quality of life (HRQL) as reported by patients and parents/caregivers.
- To assess the effect of ataluren on activities of daily living.

Exposure

- To assess long-term ataluren plasma exposure.

3.3. Clinical Endpoints

Primary

- Safety profile characterized by type, frequency, severity, timing, and relationship to ataluren of any adverse events or laboratory abnormalities

Secondary

Physical

- Change in ambulation as measured by the 6MWT
- Change in proximal muscle function as assessed by timed function tests (time to rise from supine position, time to run 10 meters, and time to climb/descend 4 stairs)
- Change in physical function as assessed by the North Star Ambulatory Assessment

- Change in motor performance of the upper limb as measured by the Performance Upper Limb (PUL)

Pulmonary function

Change in pulmonary function as measured by spirometry (eg. FVC, FEV1)

Patient-Reported Outcomes

- Change in patient- and parent/caregiver-reported HRQL as measured by the PODCI Transfer/Basic Mobility and Sports/Physical Functioning scores
- Change in patient and parent/caregiver reported activities of daily living

Exposure

- Pre-dose ataluren plasma concentrations prior to morning ataluren administration at each clinic visit as assessed by a validated bioanalytical method

Safety

- Change from baseline in other safety parameters (eg, vital signs)

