7.20. PODCI Questionnaire

HRQL will be measured via the Pediatric Outcomes Data Collection Instrument (PODCI) domains of Transfers/Basic Mobility and Sports/Physical Functioning. The PODCI questionnaire will be available in all languages relevant for this study and will be completed by the parent/caregiver. If possible, the same parent/caregiver should complete the questionnaire each time. The PODCI questionnaire will be completed during Screening/Baseline on Visit 1, Week 12 (Visit 2), Week 24 (Visit 3), Week 36 (Visit 4), Week 48 (Visit 5), Week 60 (Visit 6), Week 72 (Visit 7), Week 84 (Visit 8), and Week 96 (Visit 9) Week 108 (Visit 10), Week 120 (Visit 11), Week 132 (Visit 12), Week 144 (Visit 13 - End-of-Treatment/Premature Discontinuation). Please refer to the Study Manual for further details on how to administer the PODCI questionnaire.

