10.5.3. North Star Ambulatory Assessment (NSAA)

The NSAA consists of 17 activities, each scored as 0, 1, or 2. The sum of these 17 scores will be used to form a total score. The changes from baseline will be described by patient and visit and summarized by visit and overall.

10.5.4. Pediatric Outcomes Data Collection Instrument (PODCI) Transfers/Basic Mobility and Sports/Physical Functioning scores

The two PODCI domains (transfers/mobility and sports participation) each provide a numerical score from 0-100. Changes from baseline will be described by patient and visit and summarized by visit and overall.

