13.4.6. Pediatric Quality of Life Instrument

Health-related quality of life measurement has been increasingly used as an essential health outcome measure in clinical trials involving children with neuromuscular disorders. Generic health-related quality of life instruments have been used most frequently as patient-reported outcome measures; however, these measures may be inadequate in terms of sensitivity for detection of change induced by a treatment [McDonald 2010c]. For this study, the PODCI domains of transfers/basic mobility and sports/physical function have been selected to obtain parent/caregiver information relating to HRQL. In a study by McDonald 2010c, these domains were shown to have a close association with disease progression and clinical outcome measures historically employed in clinical trials of ambulatory boys with DMD.

The PODCI questionnaire will be available in all languages relevant for this study and will be completed by the parent/caregiver. If possible, the same parent/caregiver should complete the questionnaire each time.

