## **5. STATISTICAL ANALYSIS**

### **5.1. General Statistical Considerations**

Summary tables for continuous variables will contain the following statistics: n, mean, standard deviation, standard error, 95% confidence intervals (CIs) on the mean, median, minimum, and maximum. Summary tables for categorical variables will include N, n, and percentages. In by-visit summaries, the analysis visits will be derived via visit mapping windows.

For descriptive summary tables, the all data will be analyzed and displayed by ambulatory status (ambulatory or non-ambulatory) at baseline, unless specified otherwise. Where applicable, the summary data (mean, standard error) will be presented in graphical form of against time of visit.

By-patient listings will be created for each CRF module. The data will be listed by center/subject ID and visit.

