### **5.8.6. Pediatric Outcomes Data Collection Instrument (PODCI)**

The two PODCI domains (transfers/mobility and sports participation) each provide a numerical score from 0-100. The PODCI domain scores and changes from baseline will be summarized by visit for ambulatory subjects.

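### The HRQL endpoint is labelled patient- and parent-reported, but only parents complete the PODCI; and the SAP, without declaring it, plans no PODCI summary for boys non-ambulatory at entry

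*Protocol*

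**What the plan says.** **Objective and endpoint.** Protocol 3.2 states the objective as "To determine the effect of ataluren on health-related quality of life (HRQL) as reported by patients and parents/caregivers". Protocol 3.3 lists the matching endpoint under Patient-Reported Outcomes: "Change in patient- and parent/caregiver-reported HRQL as measured by the PODCI Transfer/Basic Mobility and Sports/Physical Functioning scores". SAP 3.2 and 3.3 repeat both.

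**Collection.** Protocol 7.20 says the questionnaire "will be completed by the parent/caregiver", by the same person each time where possible. The rationale in Protocol 13.4.6 says that the two domains "have been selected to obtain parent/caregiver information relating to HRQL". Protocol Table 3 schedules the PODCI at baseline and at all 12 treatment visits, with no condition on walking ability.

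**Analysis.** Protocol 10.5.4 gives the PODCI the same rule that 10.5.3 gives the NSAA: "changes from baseline will be described by patient and visit and summarized by visit and overall". SAP 5.8.6 is narrower: "The PODCI domain scores and changes from baseline will be summarized by visit for ambulatory subjects". SAP 5.1 sets the general rule that descriptive data are "displayed by ambulatory status (ambulatory or non-ambulatory) at baseline, unless specified otherwise". SAP 1 says that the SAP prevails where it conflicts with the protocol.

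**The concern.** There are two separate mismatches.

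The first is about who reports. The endpoint names two reporters, and the procedure supplies one. If the results are tabulated under the heading as written, open-label proxy scores from parents would be read as including the boys' own view of their quality of life.

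The second is about who is summarised. The HRQL objective covers all boys in the extension, but the governing analysis covers only those who are ambulatory. A reader of the tables would see no HRQL summary for the most advanced patients, and nothing in the SAP would tell him that this departs from the protocol.

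What is at stake is the scope of a descriptive secondary claim: whose report it is, and which boys it describes.

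**Working it through.** No sample size, power or event count bears on this point, and the plan gives no figure to reproduce. The check is a comparison of sections.

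**Reporter**

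1. Reporters promised: patients and parents/caregivers (Protocol 3.2 and 3.3; SAP 3.2 and 3.3).
2. Reporter supplied: parent/caregiver (Protocol 7.20 and 13.4.6).
3. Other HRQL instruments: none in Protocol Table 3. The daily-living and symptom survey may be answered by the patient (Protocol 7.19), but it serves its own objective and endpoint.
4. Scheduled PODCI administrations in Protocol Table 3: 1 baseline + 12 treatment visits = 13. Assigned to the patient: 0. (SAP Table 1 shows no mark at Week 108, which would make it 12; the patient count is still 0.)
5. The baseline form may be carried over from the double-blind study when the two visits fall within 14 days. These documents do not say who completed it there. This does not matter for the conclusion: with no patient-completed form after baseline, no patient-reported change can be computed.
6. The rule that the SAP prevails does not settle the matter, because the SAP repeats the two-reporter wording and does not say who completes the form.

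**Population**

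1. Protocol 3.2 limits three physical objectives to boys who are ambulatory or able to do the test. The HRQL objective in the same section has no such limit.
2. Protocol Table 3 and Protocol 10.5.4 are also unrestricted, and SAP 4 takes all treated subjects as the efficacy population.
3. SAP 5.8.6 restricts the summary to ambulatory subjects. It gives no time point for that status, so the SAP 5.1 default applies: status at baseline.
4. It follows that boys non-ambulatory at extension entry have no planned PODCI summary. Their data are still collected, and SAP 5.1 provides by-patient listings of every CRF module.
5. Such boys are foreseen. Protocol 7.5 gives a height surrogate for non-ambulatory patients from Visit 1, and SAP 5.2, 5.3 and 5.6 split tables by ambulatory status at entry.
6. SAP 7 declares two changes from the protocol: removal of the supportive 6-minute walk analyses and of all paired t-tests. The PODCI restriction is not among them.

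**Size.** Let p be the share of boys non-ambulatory at entry, and let dA and dN be the mean changes in the ambulatory and non-ambulatory groups. The overall mean change is (1 − p) × dA + p × dN. It differs from the ambulatory-only figure by p × (dN − dA). The documents give none of p, dA or dN, so neither the size nor the direction of the difference can be stated.

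**The case against.** **The restriction has a plausible reason.** Protocol 13.4.6 supports the two domains by a study in ambulatory boys, and both domains concern mobility and physical activity. The SAP matches other instruments to walking status: 6-minute walk, timed tests and NSAA for ambulatory boys (5.8.3 to 5.8.5), upper-limb assessment for non-ambulatory boys (5.8.8). This stands as a possible justification. But the SAP does not state it, and the protocol still collects the PODCI from everyone and plans to summarise it without restriction.

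**Little is claimed.** The study has no formal hypothesis (Protocol 10.1), parent completion is disclosed twice, and SAP 5.8.6 itself makes no patient-reported claim. The daily-living survey can carry some patient input and is summarised for all subjects (SAP 5.8.9). This limits the importance of the point but does not correct the endpoint wording.

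**A stronger reading to avoid.** A reader might infer that each boy leaves the PODCI summary when he stops walking, so that the mean looks preserved while the losers of ambulation disappear. The documents do not support this. The SAP 5.1 default is status at baseline, and 5.8.6 does not override it. SAP 5.8.5 points the same way: it scores NSAA activities as zero on loss of ambulation and then summarises ambulatory subjects, which makes sense only if those boys stay in the group. Boys who stop walking on study therefore most likely remain in the PODCI summary. A reader might also infer that the HRQL objective fails altogether. It does not: parent-reported HRQL in boys ambulatory at baseline can be described as planned.

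**Conclusion.** Both mismatches hold, at modest weight. The patient-reported part of the HRQL objective and endpoint has no data source: 0 of 13 scheduled PODCI administrations are assigned to the patient. The parent-reported part is intact. The SAP also leaves boys non-ambulatory at extension entry without a PODCI summary, contrary to the unrestricted Protocol 10.5.4 and without a declaration in SAP 7; their data survive in listings.

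The second conclusion rests on reading the ambulatory group in SAP 5.8.6 as status at baseline, which the general rule supports but 5.8.6 does not say. The number of boys affected cannot be derived from the documents. This is a secondary, descriptive endpoint, so the consequence is a mislabelled and incompletely reported result. The primary safety objective is untouched.

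**What to change.** 1. Restate the objective and endpoint in Protocol 3.2 and 3.3 and in SAP 3.2 and 3.3 as parent/caregiver-reported HRQL, and make no patient-reported HRQL claim. The sponsor has decided to discontinue the study (SAP 5.2), and a protocol amendment needs IRB/IEC review (Protocol 12.2). If the protocol is not amended, make the statement in the SAP, which prevails, list it in SAP 7, and carry it into the study report.
2. In SAP 5.8.6, summarise both PODCI domain scores and their changes from baseline by visit, overall and by ambulatory status at baseline. State explicitly that each boy stays in his baseline group after losing ambulation. This restores agreement with Protocol 10.5.4. If the sponsor prefers to keep the restriction, SAP 7 should declare it and give the reason.

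The cost is a change of wording and a few extra columns in one table, from data already collected. The endpoint claim becomes narrower, and the overall mean change may look less favourable than the ambulatory-only figure.
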